10.1 Disposition of Participants and Discontinuations

- Total number of participants screened (i.e. participants who gave informed consent)
- Number of subjects who excluded from the trial prior to randomisation / enrolment, overall and grouped by the main reason (e.g. did not meet eligibility criteria, withdrawal of consent, etc.).

- Number of randomised / enrolled subjects, overall and grouped by infection severity (i.e. light, moderate/heavy), cohort as well as analysis set.
- Number of randomised / enrolled subjects who discontinued the trial after randomisation / enrolment, overall and grouped by cohort as well as main reason for discontinuation (e.g. adverse event, lost to follow-up, etc.).
- Number of randomised / enrolled subjects who completed the trial, overall and grouped by cohort. Only those subjects with *End of Study* visits, not due to early withdrawal, will be considered as completed the trial.
- Number of subjects in the mITT, PP, SCR, SAF analysis populations

The number and percentage of participants in each of the above disposition categories will be presented by group (cohort/treatment) and overall. Percentages will be presented with respect to the number of enrolled/randomized participants.

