-  Pre screening will be conducted in the villages. For Cohorts 1 through 3, only children who are positive for *S. mansoni* and negative for *S. haematobium* will be transferred to the hospital for further screening. For Cohort 4, only children who are positive for *S. haematobium* and negative for *S. mansoni* will be transferred to the hospital for further screening.
-  If the participant, for logistical or social reasons, has to remain in hospital an additional night, the confinement may end up to 24 hours after dosing. At end of confinement, vital signs will be recorded and a physical examination performed.
-  Follow-up of Adverse Event (AE), if required.
-  POC-CCA cassettes will be classified as either positive or negative, according to the manufacturer's instructions, with further stratification depending on the strength of the color reaction. Thus, positive cassettes will be classified as + 1 (when result line is easy to see but still weak), + 2 (when result line is dark, but lighter than the control line) or + 3 (when result line is as dark as or darker than the control line).
-  For Cohorts 1 through 3 only
-  Cohort 1 to 3: two stool samples collected within 5 days during the pre screening period. Three Kato-Katz smears will be prepared from each of the stool samples to determine *S. mansoni* egg counts. For Cohort 4: a stool sample will be collected during the pre screening period. Two Kato Katz smears will be prepared from the sample to evaluate the presence of *S. mansoni* eggs.
-  For Cohorts 1 through 3 only. A stool sample will be collected between Day 17 to 21 days after dosing and another one within 5 days thereafter.
-  For Cohorts 1-3, one urine sample (about 10 mL) will be filtered through a filter mesh and the mesh examined under the microscope to exclude the presence of *S. haematobium* eggs. For Cohort 4: three urine samples (about 10 mL each), collected within 5 days, will be filtered through a filter mesh and the mesh will be subsequently examined under the microscope for *S. haematobium* egg count.
-  Cohort 4 only in case treated with 60 mg/kg L-PZQ ODT.
-  Malaria Rapid Diagnostic Test can be done at discretion of investigator during pre screening.
-  Before PK samples are taken.
-  Height only at screening

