#### 4.4 End of Study Definition

A participant has completed the study if he/she has completed all study parts, including stool (Cohorts 1, 2, and 3) or urine (Cohort 4) sampling at the scheduled follow-up visits.

The end of the study is defined as the date of the End-of-study visit (or Extended Follow-up visit urine collection at Week 5 for Cohort 4) of the last participant.

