8.2 Definition of Analysis Populations and Subgroups

Screening Analysis Population (SCR)

The Screening analysis population includes all participants who signed the informed consent.

Intention-to-Treat (ITT)

For the purposes of this trial the ITT analysis set described in the protocol and the safety analysis set described below are considered equivalent. For this reason, the safety analysis set will be utilized for ITT and safety analysis purposes.

Modified ITT Analysis Population (mITT)

The modified ITT (mITT) analysis population will include all enrolled participants who receive one dose of treatment and have baseline measurement. Children who require malaria treatment after enrollment in the study will not be included in the mITT population. The primary analysis of this study will be performed on the mITT population.

Per Protocol Analysis Population (PP)

Per-protocol (PP) Analysis population includes all participants who are in the mITT population and have one post baseline measurement for Cohorts 1, 2, 3 and 4a, and two post baseline measurements for Cohort 4b, without any clinically important protocol deviations. Details of the

criteria for exclusion from the PP population are provided below. An additional determination will be made prior to database lock, based on a review of data accrued during the conduct of the study.

Participants who meet any one of the following criteria will be excluded from the PP:

- Inclusion/exclusion violations
- Subjects that develop withdrawal criteria whilst on the study, but are not withdrawn
- Subjects that receive the incorrect treatment
- Subjects that receive any prohibited medications/foods/fluids as outlined in Sections 5.3, 6.5.2 and 6.5.3 of the protocol;
- Any missed doses of IMP
- Any medical condition that may modify the pharmacokinetic profile of the IMP or compromise the natural immunity of the subject
- End-of-study stool (C1-C3) samples or urine samples (C4) required for assessing the primary endpoint are missing or collected out-of-window

Safety Analysis Population (SAF)

The Safety analysis population will include all participants who receive a dose of study treatment. Participants will be analyzed according to the actual treatment they receive.

Pharmacokinetic Analysis Population (PKP)

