| Primary (mITT) | 
At each assessment visit after treatment, clinical cure is defined as no parasite eggs in the urine samples.
 
Egg counts will be determined by urine examination using the urine filtration technique: The first sample will be collected during the pre screening period (Day -28 to Day -1) and the second and the third one within a maximum of 5 days thereafter as baseline. At the End-of-Study visit (between Day 17 and 21) Cohort 4 participants will be asked to provide three urine samples (about 10 mL each): the first one will be collected within the 17 to 21-day window and the other two within a maximum of 5 days following collection of the 1st sample, for analysis by the filtration method.
 
Similarly, at the Extended Follow-up
 | 
No hypothesis testing will be performed. Point estimates and corresponding two-sided 95% CIs will be determined.
 
Subjects cured of infection during the trial will be labelled as "responders". At each of the End of Study visit (17 to 21 days after treatment, according to the eCRF page "End of Study (Day 17 to Day 21)") and the Extended Follow-up visit (35 to 40 days after treatment, according to the eCRF page "Extended Follow-up (Day 35 to Day 40)"), responders will be defined as subjects with no parasite eggs urine samples, (as determined by urine filtration method)
 
Responders and non-responders will be coded as follows:
 
 For responders, response = 1 For non-responders, response = 0 
The proportion of responders in each cohort will be determined based on a binomial distribution. Exact 95% CIs will be calculated based on the Clopper-Pearson method. The PROC FREQ procedure in SAS will be used with the appropriate BINOMIAL and EXACT statements for point estimates and corresponding 95% CIs.
 
Point estimates and corresponding 95% CIs will be presented for cure rate, in terms of proportion of responders, by cohort. Response will be listed by cohort and subject. Estimates of cure rate will be presented graphically in the form of forest plots presenting point estimates and 95% CIs.
 
Results will be presented for each analysis set.
 | 
If the End of Study or Extended Follow-up visit egg count is missing, carried forward for imputation. According to this rule subjects with missing egg count data at post-treatment assessment will be considered as non-responders at the End-of-study visit. For cohort 4b, if the assessment at Extended Follow-up visit is missing, the assessment result at End-of-study visit will be carried forward.
 |

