| 
Primary (PP)
 | | | 
No Imputation will be done.
 |

| | | | |
|--|---|---|--|
| | | 
Point and interval estimates of ERR_A, ERR_G and proportion of individuals with $iERR \geq 90\%$ will be presented by treatment group. 95% CIs of these 3 parameters will be calculated by bootstrapping (using SAS procedure SURVEYSELECT). Mean Kato-Katz egg counts will be listed by cohort and subject and time point. Estimates of ERR_A, ERR_G and $iERR$ will be presented graphically in the form of boxplots, by cohort.
 
Results will be presented for each analysis set.
 | |
| Secondary endpoint: Egg Reduction Rate (ERR) in children 2 to 3 years of age and in infants and toddlers 3 months to < 24 months of age infected with S. mansoni (Cohorts 2 and 3, respectively) and in children 3 months to 6 years of age infected with S. haematobium (Cohort 4). | | | |
| Primary (mITT) See 14.1.2 for details about analysis for participant 3 to 24 months of age (Cohort 3). | ERR from pre treatment to 17 to 21 days after treatment, using parasite egg counts as determined by the Kato-Katz method for Cohorts 2 and 3 and the urine filtration method for Cohort 4. Additionally, for Cohort 4b participants ERR from baseline to 35 to 40 days after treatment, using parasite egg counts as determined by the urine filtration method, | Same as Cohort 1 (Secondary analysis). | 
If the End of Study egg count is missing, it will be imputed using the Last Observation Carried Forward (LOCF) approach. Subjects with all post-baseline egg counts missing will be considered non-responders.
 
For cohort 4b, if egg counts is missing only at Extended Follow-up visit, it will be imputed by taking the value from End-of-study visit.
 |
| Secondary endpoint: cure rate as demonstrated with use of the commercially available point-of-care circulating cathodic antigen (POC-CCA®) test (Cohorts 1, 2, and 3). | | | |

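### SAP 10.1 counts a 60 mg/kg (4b) child as a completer after the Day 17–21 visit, although protocol 4.4 also requires the Day 35–40 urine sampling

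*SAP*

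**What the plan says.** **Completion rule in the SAP.** SAP 10.1 (Disposition of Participants and Discontinuations) counts as completers only participants with End of Study "visits, not due to early withdrawal, will be considered as completed the trial". It does not mention the Extended Follow-up visit or require a sample.

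**Completion rule in the protocol.** Protocol 4.4 (End of Study Definition) states: "A participant has completed the study if he/she has completed all study parts, including stool (Cohorts 1, 2, and 3) or urine (Cohort 4) sampling". The sentence then ties that sampling to the scheduled follow-up visits, in the plural. The same section defines the end of the whole study by the last participant's End-of-Study visit, "or Extended Follow-up visit urine collection at Week 5 for Cohort 4", so the two visits are kept distinct.

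**Who has the later visit.** The footnote to the Extended Follow-up column in the protocol's Schedule of Activities (1.3) reads: "Cohort 4 only in case treated with 60 mg/kg L-PZQ ODT". SAP section 9 calls this treatment group 4b.

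**What the SAP means by the End of Study visit.** SAP 14.2 assesses Cohort 4 response separately at two visits. The first is introduced as "At each of the End of Study visit (17 to 21 days after treatment". The second is the Extended Follow-up at Day 35–40, which has its own eCRF page.

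**Where the SAP was adapted for 4b.** The per-protocol definition in SAP 8.2 requires "two post baseline measurements for Cohort 4b". For the egg reduction rate (ERR) in 4b, SAP 14.2 says "if egg counts is missing only at Extended Follow-up visit, it will be imputed by taking the value from End-of-study visit", and it applies a matching rule to the cure rate.

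**The concern.** The Day 35–40 visit was added by protocol amendment 1.2. The SAP's per-protocol definition and imputation rules allow for it, but the completion rule in SAP 10.1 does not. Followed literally, that rule gives a 4b completer count that disagrees with the protocol's definition.

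The Day 35–40 cure rate and ERR are named secondary endpoints, and a missing value there is filled from Day 17–21 in the imputed analysis. A reader of the study report will look first to the disposition table to see how many children were followed to that time point. The completer row should answer that question, and as written it does not.

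There is also a smaller mismatch in the other groups. Protocol 4.4 requires the stool or urine sampling, while SAP 10.1 requires only the visit. A child who attends but gives no sample is a completer in one document and not in the other.

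**Working it through.** The plan states no completion figure to reproduce. The check is a comparison of the two rules, followed by a simple count.

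**Step 1: apply each rule to one child.** Take a 4b child who attends as scheduled on Day 18, gives the required urine samples, and cannot be reached afterwards.

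- *Protocol 4.4:* the Day 35–40 sampling was scheduled and not done, so the child is not a completer.
- *SAP 10.1, completed row:* the child has an End of Study visit, and it was not held because of early withdrawal. The child is a completer.
- *SAP 10.1, discontinued row:* protocol 7.3 treats an unreachable child as withdrawn, and SAP 10.1 counts discontinuations after enrolment by main reason, with loss to follow-up as an example. The child also belongs here.

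The exclusion for early withdrawal does not catch this case, because the visit took place before the loss. SAP 10.1 has no rule for choosing between the two rows.

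A 4b child who stays in contact but gives no Day 35–40 urine is likewise a completer in the SAP and not in the protocol. That child need not appear in the discontinued row at all.

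**Step 2: size per child.** Protocol 9.2 plans 60 children at the final Cohort 4 dose, and the footnote to protocol 4.1 records the decision to move to 60 mg/kg. Percentages in SAP 10.1 are based on participants enrolled or randomized. Each affected child therefore adds 1/60 = 1.7 percentage points to 4b completion.

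**Step 3: illustration.** The documents give no rate of loss between Day 21 and Day 35, so the rates below are assumptions. All 60 children are taken to attend Day 17–21.

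| Assumed loss after Day 17–21 | Children lost | Completers, SAP 10.1 | Completers, protocol 4.4 |
|---|---|---|---|
| 1 child | 1 | 60/60 (100%) | 59/60 (98%) |
| 5% | 60 × 0.05 = 3 | 60/60 (100%) | 57/60 (95%) |
| 10% | 60 × 0.10 = 6 | 60/60 (100%) | 54/60 (90%) |
| 20% | 60 × 0.20 = 12 | 60/60 (100%) | 48/60 (80%) |

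If the lost children are also entered as discontinued, the two rows exceed the number enrolled. At 10% loss, 60 completed plus 6 discontinued makes 66 entries for 60 children.

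**Step 4: does anything else use the flag?** The mITT set depends on dosing, a baseline measurement and no malaria treatment. The per-protocol set depends on post-baseline measurements and deviations. Imputation depends on whether the egg count is missing. None refers to completion status, so no cure rate, ERR or confidence interval changes.

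**The case against.** Several points on the other side have force.

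- *The loss is still reported.* A 4b child lost after Day 21 fits the discontinued row. Missing Day 35–40 data also show up in the reasons for per-protocol exclusion (SAP 8.2 and 10.2.2) and in the mITT tables, which are presented with and without imputation (note to SAP 14.2). This stands. A reader might infer that attrition disappears, or that imputed Day 35–40 results could pass as observed. The documents do not support that.
- *4b is shown separately.* Some bullets in SAP 10.1 group by cohort, and a reader might infer that 4b is merged with the 50 mg/kg children and any shortfall diluted. However, the section closes by presenting every category by cohort or treatment group and overall, and SAP section 9 makes 4a and 4b separate treatment groups. That stronger reading fails.
- *It is not an undeclared change of analysis.* A reader might set this against SAP section 7, which declares no changes. That statement concerns planned analyses, whereas protocol 4.4 is a study-conduct definition outside the protocol's statistical section.
- *The wording is not watertight.* The SAP sentence begins with the word only, so it could be read as a necessary condition and not a sufficient one. SAP 15.2.1 also mentions an End of Study eCRF page that records the reason for not completing, which might capture final status. These are fair caveats. But SAP 10.1 gives no other criterion and speaks of visits, and SAP 14.2 ties the End of Study visit to Day 17–21.

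**Conclusion.** The completion rule in SAP 10.1 is wrong as written for 4b, and the point is minor. It overstates the 4b completer count, and the overall count with it, by one for each child who has the Day 17–21 visit but not the Day 35–40 sampling. That is 1.7 percentage points per child in 4b if the planned 60 are enrolled. The total cannot be stated because the documents give no loss rate. The completed row can also overlap the discontinued row.

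The conclusion rests on two readings: that the End of Study visit in SAP 10.1 means Day 17–21, as in SAP 14.2, and that only 60 mg/kg children are scheduled for Day 35–40, as the Schedule of Activities footnote says. The defect is confined to the disposition table. The primary endpoint in Cohort 1 and all efficacy estimates are unaffected.

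**What to change.** In SAP 10.1:

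- Define completion as in protocol 4.4. For 4b, require both the End of Study and Extended Follow-up visits with the required urine samples. For all other groups, require the End of Study visit with the required stool or urine samples.
- State that the completed and discontinued rows are mutually exclusive.
- Add a row for 4b children seen at Day 17–21 with no Day 35–40 sample, with the reason.

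The cost is a wording change and one disposition derivation from data already collected. The reported 4b completion rate may be slightly less favourable.

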10.2 Protocol Deviations

10.2.1 Important Protocol Deviations

The following summary tables and listings of important protocol deviations will be provided:

- Frequency table per reason of important protocol deviations by treatment group.
- Listing of important protocol deviations

10.2.2 Reasons Leading to the Exclusion from an Analysis Population

For participants excluded from the mITT and PP, the reasons for exclusion will be summarized and listed:

- Frequency table of deviations from each cohort, grouped by reason of important protocol deviations, including COVID-19 as a reason, if applicable
- Listing of reasons of exclusion

11 Demographics and Other Baseline Characteristics

If not stated otherwise, summaries will be presented on the SAF and on the mITT analysis population, by treatment group and overall.

11.1 Demographics

Demographic characteristics will be summarized using the following information from the Screening/Baseline Visit CRF pages.

- Demographic characteristics

- Gender: male, female
- Race/Ethnic: Black or African American, Asian, Native Hawaiian or other Pacific Islander, American Indian or Alaska Native, White, other, not collected at site.
- Age (months and years): summary statistics
- Age categories:
 - 4 to 6 years of age
 - 2 to 3 years of age
 - 3 to < 24 months of age
- Height in cm at Baseline: summary statistics
- Weight in kg at Baseline: summary statistics
- Body-mass index (kg/m²) at Baseline: summary statistics

Specifications for computation:

- Age [months and years]:
 - Age [in years] will be calculated as follows:
(date of given informed consent - date of birth + 1) / 365.25
 - Age [in months] will be calculated as follows:
(date of given informed consent - date of birth + 1) / 30.4375
 - In case of missing day for at least one date, but month and year available for both dates:
Missing day will default to the first day of the month, i.e. 01
 - In case of missing month for at least one date, but year available for both dates:
Missing month will default to the first month of the year, i.e. January or 01

In all tables, age will be summarized in years.

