#### 9.4.1 Efficacy Analyses

The primary efficacy analysis will be performed on the mITT population of Cohort 1. The primary endpoint of cure rate will be calculated as the percentage of egg-positive participants at baseline who become egg-negative after treatment (as assessed by the Kato-Katz method). The exact 95% CI will be calculated based on the Clopper-Pearson method. Cohorts 2, 3, and 4 will be analyzed similarly.

The secondary endpoint of cure rate by POC-CCA® (Cohorts 1, 2, and 3) will be analyzed in the same manner as the primary endpoint, with proportion cured and its 95% CI.

The secondary endpoint of ERR will be analyzed for each of the cohorts and treatment group (Cohort 1) as group-based ERR (arithmetic and geometric) and as individual ERR (arithmetic and geometric).

Subgroup analyses will also be conducted by severity of infection (light vs. moderate/heavy infection stratification factor), country and gender. In Cohort 4, subgroup analyses will also be done by specific age groups (e.g., 3 months to 24 months of age, 2 to < 4 years of age, 4 to 6 years of age).

Sensitivity analyses may be performed on the ITT population of Cohort 1, to determine the impact of participants requiring malaria treatment, and on the PP population of Cohort 1, to assess the impact of any protocol deviations (such as completing study assessments outside the Day 17 to 21 window).

Analysis of Cohort 3 will be a pooled analysis, including the mITT population from this study and the mITT population for participants 3 to 24 months of age in the Phase II study MS200661-0005 (Cohorts 8 and 9). A logistic regression model with adjustment for study and site variability will be used to estimate cure rate.

Analysis of Cohort 4 will be performed only on the mITT population and using the same methods as for Cohort 1.

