The PK Analysis Population is a subset of the SAF population and will consist of all participants who receive at least one dose of active IMP and provide at least one measurable post-dose concentration. A measurement below lower limit of quantification (BLQ) is considered a valid measurement. Participants will be analyzed according to the actual treatment they received. Subjects in this analysis population may not have taken prohibited medications/foods/fluids, and may not have experienced any diarrhea or vomiting after IMP administration.

Additional Subgroup Analysis Populations

Subgroup analyses will be performed on subgroups as defined below.

The final parameterization will be updated and fixed at the Data Review Meeting at the latest and documented in an amendment to this IAP if different from the following definition.

The following subgroups will be defined:

- Age
 - 4 to 6 years of age (Cohorts 1 and 4)
 - 2 to 3 years of age (Cohorts 2 and 4)
 - 3 to < 24 months of age (Cohorts 3 and 4)
- Gender

- Male
- Female
- Severity of infection (as assessed at Pre-screening [D-28 to D-1])
 - *S. mansoni* infection
 - Light infection: 1 - 99 eggs per gram of faeces
 - Moderate/heavy infection: ≥ 100 eggs per gram of faeces
 - *S. haematobium* infection
 - Light infection: < 50 eggs/10 mL of urine
 - Heavy infection: ≥ 50 eggs/10 mL of urine
- Note: In summary tables, *S. haematobium* heavy infection will be classified as Moderate /Heavy when being presented side-to-side with other cohorts.
- Trial center/country
 - PPD
 - [REDACTED]

9 General Specifications for Data Analyses

Study intervention groups

Study intervention groups are defined and labelled as Biltricide® and L-PZQ ODT.

Unless otherwise indicated all analyses will be presented separately for treatment groups. Specifically, Cohorts 1a and 1b will be presented separately in all tables. In general, in this IAP the term “cohorts” represents Cohorts 1, 2, 3 and 4, whereas the term “treatment groups” stands for Cohorts 1a, 1b, 2, 3, 4a and 4b with 4a and 4b representing Cohort 4 participants treated with 50 mg/kg and 60 mg/kg, respectively.

Data handling after cut-off date

Data (other than the date of death and the date last known to be alive) obtained after the cut-off will not be displayed in any listings or used for summary statistics, e.g. laboratory values of samples taken after data cut-off, AEs with onset date after data cutoff, etc. will not be included in any analysis or listing.

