14.3 Supportive Subgroup Analyses for Efficacy Analysis

Analysis set(s):

- Supportive analyses of the primary endpoint will be based on the mITT and PP analysis sets.

Clinical cure rate by subgroup:

If the End of Study Kato-Katz egg count is missing, it will be imputed using the LOCF approach. Subgroup analyses the study will be performed, by the following subgroups:

- Age category (Cohort 4 only)

- Gender
- Severity of infection
- Country

Descriptive statistics of cure rates for each subgroup will be estimated for each cohort.

Cure rate, in terms of proportion of responders, will be summarised by cohort and by infection severity, gender and country and listed by cohort and subject. Estimates of cure rate will be presented graphically in the form of a forest plots presenting point estimates and 95% CIs, by treatment group and subgroup. Forest plot by age group is needed for Cohort 4 only. Cure rates will be presented as percentages, not proportions, i.e. *cure rate* × 100.

For mITT analysis tables will be presented with imputation and without imputation.

15 Safety Analyses

Safety and tolerability assessments:

- Occurrence, nature, severity and outcome of adverse events (AEs),
- Occurrence of treatment-related AEs
- Changes in laboratory safety parameters (hematology, biochemistry, urinalysis) and vital signs (body temperature, blood pressure and pulse rate)

Analysis set(s):

- SAF analysis set.

Safety analyses will be done on the SAF analysis set and according to the as-treated principle. This section includes specifications for summarizing safety endpoints that are common across clinical trials such as AEs, laboratory tests, reactions to the IMP and vital signs.

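### The January default for an unknown birth month (SAP 11.1) can only overstate age, by about half a year on average; this affects descriptive age groups, not the primary endpoint

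*SAP*

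**What the plan says.** SAP 11.1 computes age as consent date minus birth date plus one day, divided by 365.25 for years or 30.4375 for months. Two rules cover incomplete dates. When month and year are known, "Missing day will default to the first day of the month, i.e. 01". The second rule applies as follows: "In case of missing month for at least one date, but year available for both dates". It reads: "Missing month will default to the first month of the year, i.e. January or 01". Neither rule has an exception or a bound.

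The age categories are 3 to <24 months, 2 to 3 years and 4 to 6 years (SAP 8.2 and 11.1). They are tabulated in the demographics. For efficacy, age is a subgroup factor in Cohort 4 alone (SAP 14.3: "Forest plot by age group is needed for Cohort 4 only"). Protocol 9.4.1 gives the Cohort 4 groups as "3 months to 24 months of age, 2 to < 4 years of age, 4 to 6 years of age". SAP 15.4 sets vital-sign ranges that change at 12 and 24 months and stop at 6 years.

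Neither document says how many birth dates are expected to be incomplete, and no sensitivity analysis is planned for them.

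**The concern.** A first-of-the-year default is harmless only if its error has no consistent direction or is small against the categories it feeds. Here neither holds. The earliest possible birth date gives the largest possible age, so errors from different children add up instead of cancelling. Half a year is also large beside a youngest group that is 1.75 years wide.

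Cohort 4 (60 to 90 children, two doses) is not divided into age cohorts, so its cure rates by age depend on each child's age, and SAP 11.1 holds the only age formula in the plan. In small subgroups a few moved children can change an estimate. In the demographics tables a Cohort 2 or 3 child could appear in a category outside the cohort's own age band. In the 3 to 24-month tables pooled with Phase II (SAP 14.2.1), ages of 24 months or more could appear.

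Other first-of-the-year start-date defaults in the SAP (medical history, medications and adverse events in 11.2, 12 and 15.1) carry exceptions that use other known facts. The birth-date rule has none, although eligibility limits each child's possible age.

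**Working it through.** The plan gives no figure for the effect of this rule, so there is none to reproduce.

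**Inputs from the documents.** Imputed birth date 1 January (SAP 11.1). Group limits 0.25 to <2, 2 to <4 and 4 to 6 years (SAP 8.2, Protocol 9.4.1). Planned sizes 150, 30, 25 to 65 and 60 to 90 for Cohorts 1 to 4 (Protocol 1.1).

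**Assumptions not in the documents.** Births uniform over the year, ages uniform within group, consent dates uniform over the year, and 4 to 6 years read as under 7. The day rule is written only for a known month; it is taken to apply together with the month rule.

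**Mean error.** The overstatement S runs from 0 to 364 days, mean 182 days (182.5 in a leap year); 182/365.25 = 0.50 year. If the day is known and only the month is missing, the mean is 167 days, or 0.46 year. The difference, about 15 days, is the part due to the day default.

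**Share crossing the upper limit of a group of width w.** This is E[S]/w = 0.5/w. For consent at fraction t of the year it is (1 − t)/w. Mean t is 0.125 in January to March and 0.875 in October to December.

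| True age group | w (years) | All year | Consent Jan–Mar | Consent Oct–Dec | Moves to |
|---|---|---|---|---|---|
| 3 to <24 months | 1.75 | 0.5/1.75 = 28.6% | 0.875/1.75 = 50% | 0.125/1.75 = 7% | 2 to 3 years |
| 2 to 3 years | 2 | 0.5/2 = 25.0% | 0.875/2 = 44% | 0.125/2 = 6% | 4 to 6 years |
| 4 to 6 years | 3 | 0.5/3 = 16.7% | 0.875/3 = 29% | 0.125/3 = 4% | age 7 or more, no category |

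No child moves to a younger group. Simulation with 4 million draws per scenario agrees (28.6%, 25.0% and 16.7% over the whole year).

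**Full age range** (uniform from 3 months to <7 years, as could hold in Cohort 4). Move up a group: (0.5 + 0.5)/6.75 = 14.8%. Pass 7 years: 0.5/6.75 = 7.4%.

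**Planned cohort mix.** No Cohort 1 child can move up a group. At the smallest size, (30 × 0.250 + 25 × 0.286 + 60 × 0.148)/265 = 8.9%. At the largest, (30 × 0.250 + 65 × 0.286 + 90 × 0.148)/335 = 11.8%.

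**Unbounded mid-year default, for comparison.** The mean error is about 0. The share crossing each limit, in each direction, is 0.125/w: 7.1%, 6.3% and 4.2% for the three groups. The 7.1% downward in the youngest group would fall below 3 months.

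All percentages are of affected children, not of all children.

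**The case against.** The strongest objection is that the problem may never arise. Date of birth is collected at pre-screening and again at screening (Protocol 8), it must be in the source file (Protocol Appendix 2), and candidates are listed from census records. Age is inclusion criterion 1, down to a band defined in months, and waivers are not allowed. A toddler with no known birth month would be hard to allocate. This stands: no affected child is shown to exist, and the point concerns a contingency rule.

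The consequences are also limited. The SAP does not expressly say that the Cohort 4 age subgroups use the imputed age, and inclusion criterion 1 lists the same three bands. However, the protocol's data lists name date of birth, not an age band, and SAP 11.1 is the only age formula. The link is therefore the natural reading, though not a stated one.

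The uniform-consent assumption is weak too, since the protocol foresees a treatment period of up to 6 months. That is why the seasonal range must be shown beside the 25% and 29%.

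A reader might infer more than this supports:

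- That a quarter of all affected children change group. That share applies only below 4 years; no group lies above 4 to 6.
- That infants leave the group with the least data. No Cohort 4 age split is given.
- That the efficacy results of Cohorts 1 to 3 are distorted. They are presented by cohort, and age is not a subgroup factor there.
- That a plain 1 July default costs nothing. It can place a birth after consent or an age below 3 months, which January cannot do to an eligible child.

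**Conclusion.** The point holds as a minor one. Under SAP 11.1 a child with an unknown birth month is given the oldest possible age, about 0.50 year too old on average (0.46 if the day is known). The one-way direction and the mean do not depend on the age mix; the mean needs only births spread evenly over the year. The misclassification shares also rest on uniform ages and consent dates: 25% to 29% of affected children under 4 move up a group (6% to 50% by consent season), about 17% of those aged 4 to 6 fall outside every category, and about 15% move up over the full range (9% to 12% at the planned mix).

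The count of affected children is unknown and may be zero. What can change is the demographics tables, the descriptive Cohort 4 age subgroups and possibly which vital-sign range applies. The primary endpoint does not depend on the derived age.

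**What to change.** Amend SAP 11.1 for date of birth only:

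- Missing day: the 15th.
- Missing month: the mid-point of the birth dates still possible given the known birth year, the consent date and the eligibility age limits. The limits are the assigned cohort's age band in Cohorts 1 to 3, and 3 months to 6 years in Cohort 4. No imputed age can then be negative or ineligible.
- Cohorts 1 to 3: take the age category from the assigned cohort.

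The cost is a few lines of text and programming, with a small downside. Some affected Cohort 4 children may still be placed in the wrong group, now in either direction. The unbounded mid-year figures above (4% to 7% across each limit) indicate the order of size; the bounded rule was not simulated. SAP 14.2.1 pools Phase II derived variables directly on the premise that both studies use the same derivations. The pooled 3 to 24-month demographics must therefore apply the new rule to the Phase II children as well, or note the difference.
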